10.9.3 Time to Recurrence of the first Symptomatic/Probable UTI episode

The time (number of days) to the first recurrence of Symptomatic/Probable UTI, as well as the time to first Symptomatic UTI, will be calculated for each subject, as measured from the date of the Randomization Visit (Visit 1) to the date of first Symptomatic/Probable UTI diagnosis post-randomization. Kaplan-Meier life-table

analysis will be used to describe the survival rates and the logrank test will be used to compare the two treatment groups.

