3.2 Study Objectives

3.2.1 Primary Objective

The primary objective of this study is to evaluate the efficacy of LACTIN-V, compared to placebo, in pre-menopausal women with recurrent uncomplicated UTI.

1. To evaluate the number (percent) of subjects in each treatment group with at least one recurrence of symptomatic UTI.
2. To evaluate the efficacy of LACTIN-V, compared to placebo, in reducing the incidence of symptomatic UTI.
3. To evaluate the time to recurrence, in subjects receiving LACTIN-V as compared to placebo, of symptomatic UTI

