3.3 Case Definitions

3.3.1 Symptomatic UTI

Symptomatic UTI is defined as an episode with one or more UTI symptoms (dysuria, urgency, frequency) prompting evaluation and treatment, with a positive urine culture. A positive urine culture is defined as $\geq 10^2$ /ml of an uropathogen in these patients.

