10.3 Measurement

There are six scheduled study visits during which clinical assessment and measurements will be made in this study:

Activity	Schedule
Visit 0	Screening
Visit 1	Randomization (Day 3-10 post antibiotics)
Visit 2	Week 3
Visit 3	Week 6
Visit 4	Week 10
Visit 5	Week 14
Visit 6	Week 18

Safety will be assessed at each visit using self-reported adverse events, symptoms and pelvic examination findings. Pelvic examinations at each visit will be used to evaluate subjects for signs of irritation involving the external genitalia, cervix or vagina.

The presence of a Symptomatic UTI episode will be assessed at each visit by the investigator using the case definitions in Section 3.3. Subjects will also be queried at each study visit regarding any Probable UTI episodes, which may have occurred since the prior visit. The number of days from the date of the Randomization Visit to the date when a recurrence of UTI is first diagnosed will be used to calculate the time to UTI recurrence. A new on-study UTI (Symptomatic or Probable UTI) can only be diagnosed after the urine culture at Visit 1, or at another interim study visit after confirming resolution of the prior UTI.

Vaginal microbiota will be assessed using the Nugent Scoring System for Gram Stained Vaginal Smears at Visits 1 through 6. Vaginal cultures of total lactobacilli and *E. coli* will be evaluated at Visits 1 through 6. Colonization with the exogenous *Lactobacillus crispatus* strain CTV-05 will be evaluated by the presence or absence of CTV-05 by rep-PCR at Visits 1 through 6. Vaginal fluid specimens from each visit will be stored for assessment of shifts in the composition of vaginal microbiota using qualitative and/or quantitative DNA amplification methods. Presence and/or quantity of H₂O₂, lactic acid, and cytokines will be assessed.

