10.8 Analysis Methods

Summary statistics of frequencies, percentages, and 95% confidence intervals will be provided for categorical data. Means, standard deviations (SD), medians, and ranges (minimum, maximum) will be provided for continuous data. Chi-square test (Cochran-Mantel-Haenszel [CMH] methods), Fisher's exact test, or McNemar's test will be used for categorical variable comparisons and a t-test or rank-sum test will be used for continuous variable comparisons. Specifically, the following table lists the key variables to be analyzed by endpoint.

Table 1 **Analysis Variables and Methods**

Endpoint	Variable	Type	Statistics	Method
Primary	Percent of subjects with any Symptomatic/Probable UTI	Categorical	Frequency, Percent	95% confidence intervals
	Incidence of Symptomatic/Probable UTI	Categorical	Frequency, Percent	CMH
	Time to recurrence of first Symptomatic UTI	Numeric	Mean time to recurrence	Survival analysis, log rank test
Secondary	Change in vaginal microbiota (Nugent score)	Categorical	Frequency, Percent	Shift table (from Visit 1 to Visit 6), CMH
	Total Lactobacillus vaginal colonization	Categorical	Frequency, Percent	95% confidence interval at Visits 1-6
	Colonization with CTV-05	Categorical	Frequency, Percent	95% confidence interval at Visits 1-6

Endpoint	Variable	Type	Statistics	Method
	Total E. coli vaginal colonization	Categorical	Frequency, Percent	95% confidence interval at Visits 1-6
	Change in vaginal microbiota (DNA Amplification)	Categorical	Frequency, Percent	CMH 95% confidence interval
	H2O2, lactic acid, cytokines	Numeric	Medians, Percentiles	Wilcoxon rank-sum test
	Adverse Events, Serious Adverse Events, Symptoms, and signs of irritation on pelvic examination	Categorical	Frequency, Percent	Fisher's exact test may be used for selected AE preferred terms, symptoms or findings

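### Section 10.9.3 gives one end date, the first Symptomatic/Probable diagnosis, to two time-to-event variables, so as written the Symptomatic-only time can be ended by a Probable UTI

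*Combined protocol and SAP*

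**What the plan says.** Section 10.9.3 opens with two variables: "The time (number of days) to the first recurrence of Symptomatic/Probable UTI, as well as the time to first Symptomatic UTI, will be calculated". A single measurement rule follows, running from the Randomization Visit "to the date of first Symptomatic/Probable UTI diagnosis post-randomization". The Kaplan-Meier description and the log-rank test are then specified on that basis.

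Two other sections describe the clock. Section 10.1 item 2 ends it at the first UTI diagnosis after randomization and then lists (a) Symptomatic or Probable UTI and (b) Symptomatic UTI. Section 10.3 counts days from the Randomization Visit "to the date when a recurrence of UTI is first diagnosed will be used to calculate the time to UTI recurrence", without naming the type of UTI.

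Section 3.3 separates the two event types. A Symptomatic UTI is an episode "prompting evaluation and treatment, with a positive urine culture". A Probable UTI needs only symptoms that lead to evaluation and treatment, and can be recorded without a urine culture.

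The objective and the analysis table name the narrower event. Objective 3 in 3.2.1 reads "To evaluate the time to recurrence, in subjects receiving LACTIN-V as compared to placebo, of symptomatic UTI". The only time-to-event row in Table 1 (10.8) is "Time to recurrence of first Symptomatic UTI", analysed by log-rank test.

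**The concern.** A programmer who codes the 10.9.3 rule as it stands obtains the same date for both variables in every woman. Any woman whose first on-study episode is Probable-only then gets a Symptomatic time that does not refer to a Symptomatic UTI. The variable affected is one of the three items under the primary objective and the only log-rank row in Table 1.

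Even an analyst who sees what was meant still has a choice to make. An earlier Probable-only episode could count as an event, censor the woman, or be passed over while follow-up continues. The plan does not choose, so two competent analysts could report different results for the same primary-objective comparison, and the choice could be made after unblinding.

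**Working it through.** **1. The plan's own figure.** Section 10.4 claims more than 80% power with 250 women for a 50% reduction from 40%. Take 125 per arm (1:1, 6.2.2.1) and two-sided alpha 0.05 (assumed; not stated). The pooled SE is √(2×0.3×0.7/125) = 0.0580 and the unpooled SE is √((0.24+0.16)/125) = 0.0566. Then z = (0.20 − 1.96×0.0580)/0.0566 ≈ 1.53, and power is 93.7%. With 30% loss (87.5 per arm) it is 82.9%. The claim is a lower bound and is met.

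**2. The rule applied to three women** (hypothetical dates)

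| Course after randomization | Symptomatic time under the 10.9.3 rule | Symptomatic time evidently meant |
|---|---|---|
| Probable-only Day 20, resolution confirmed, culture-positive Day 75 | event, Day 20 | event, Day 75 |
| Probable-only Day 40, nothing later | event, Day 40 | censored at last follow-up |
| Culture-positive Day 30 first | event, Day 30 | event, Day 30 |

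The first row depends on the 10.3 condition that a new UTI can be diagnosed only once the previous one is confirmed resolved.

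**3. Illustration of size.** Inputs: 125 per arm, 40% vs 20% (10.4), no loss, exponential times, two-sided 0.05. Section 10.4 does not say which type of UTI the 40% refers to; here it is taken as Symptomatic. The Probable risk q is assumed, as the documents give none.

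- Cumulative hazards: control −ln(0.6) = 0.511; LACTIN-V −ln(0.8) = 0.223; Probable −ln(1−q), equal in both arms for now.
- Intended analysis: HR = 0.223/0.511 = 0.437; events = 125×(0.40+0.20) = 75; Schoenfeld power = Φ(½√75×|ln 0.437| − 1.96) = Φ(1.63) = 94.8%.
- Literal rule at q = 10%: hazard −ln(0.9) = 0.105; HR = (0.223+0.105)/(0.511+0.105) = 0.533; events = 125×[(1−0.6×0.9)+(1−0.8×0.9)] = 92.5; power = Φ(½√92.5×|ln 0.533| − 1.96) = 85.7%.

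| q | HR, literal rule | Events | Events that are Probable-only | Power, literal rule | Power if Probable UTI censors |
|---|---|---|---|---|---|
| 0 | 0.437 | 75 | 0% | 94.8% | 94.8% |
| 5% | 0.488 | 83.8 | 12.6% | 90.7% | 94.3% |
| 10% | 0.533 | 92.5 | 22.8% | 85.7% | 93.8% |
| 15% | 0.573 | 101.2 | 31.2% | 80.1% | 93.3% |

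**4. The assumption that drives the direction.** Let the product also act on Probable UTI, with q now the control-arm risk. At a Probable hazard ratio of 0.75, power under the literal rule is 93.5%, 92.2% and 91.1% for q = 5%, 10% and 15%. At a Probable hazard ratio of 0.437, the same as for Symptomatic UTI, the overall HR stays at 0.437 and power rises to 96.1%, 97.1% and 97.9%, because there are more events and no dilution.

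**The case against.** The strongest reply is that the intended variable can be recovered. In 10.1 item 2 each list entry can be read as supplying the UTI type for the generic first diagnosis. Table 1 and objective 3 name Symptomatic UTI. Sections 10.9.1 and 10.9.2 use the same pairing of outcomes for two distinct outputs. A rule that makes two named variables identical would also alert most analysts. The wording in 10.3 is generic and does not itself say that a Probable UTI stops the Symptomatic clock. All of this stands. A reader might infer that the trial means to use a composite end date, or that the culture-confirmed comparison will never be produced; the documents support neither.

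Uncultured episodes may also be few. Section 6.3.6 calls for urine testing for all urinary symptoms on study, 5.1 asks women to return promptly, and 6.3.7 obtains outside records. That limits the number affected but does not bring it to zero: the same 6.3.6 list is described as a guide only, and 10.3 has women asked at each visit about Probable episodes since the last one.

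Finally, some Probable UTIs may be true infections that were not cultured, and the product might prevent those too. Dilution is therefore conditional, as step 4 of the working shows.

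What the reply does not supply is a rule. Recovering the intended event does not settle how an earlier Probable-only episode is treated, and no section does.

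**Conclusion.** The stated derivation is wrong as written for one of the two variables it covers, and the handling of a preceding Probable-only episode is unspecified. It is a drafting defect in a primary-objective analysis, worth correcting before unblinding.

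Its numerical effect cannot be determined from the documents. The movement to a hazard ratio of 0.49–0.57 and power of 91–80% holds only if Probable UTI occurs in 5–15% of women, is unaffected by product, and comes on top of a 40% vs 20% Symptomatic risk. If the 40% in 10.4 already includes Probable UTI, adding 5–15% counts some episodes twice. A reader might take the illustration to show that the trial loses power or that the claim of more than 80% is wrong. It shows neither: the claim reproduces, and with an equal product effect on Probable UTI the literal rule would raise power. What would change in that case is the meaning of the result, since it would no longer be confined to culture-positive episodes.

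**What to change.** In 10.9.3, and in the matching sentence of 10.3, give each variable its own end date:

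- Time to first Symptomatic/Probable UTI ends at the first post-randomization episode of either type.
- Time to first Symptomatic UTI ends at the first post-randomization episode that meets 3.3.1 and counts as new under the 10.3 resolution rule.
- In the Symptomatic analysis, a preceding Probable-only episode is not an event and does not end follow-up. Women without a Symptomatic UTI are censored at last follow-up.
- Censoring at the Probable-only episode can be a sensitivity analysis.

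Continuing follow-up keeps the variable aligned with objective 3 and uses all observed Symptomatic episodes.

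The cost is a few sentences, with no new procedure and no change in sample size. The documents say that UTI diagnoses go on the UTI CRF (6.3.5, 6.3.6) but do not show the form, so the sponsor should check that the date, culture result and resolution of each episode can be linked in the data.

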10.10 Analysis of Secondary Endpoints

10.10.1 Shifts in Vaginal Microbiota, as Assessed by Nugent score

Significant changes in vaginal microbiota will be evaluated by the Nugent score with shift tables from Visit 1 (Day 1) to Visit 6. The Nugent score is graded as 0 to 10 and categorized as follows:

- 1 Normal, if between 0 and 3;
- 2 Intermediate, if between 4 and 6;
- 3 Bacterial vaginosis (BV), if between 7 and 10.

See Appendix A, Nugent Scoring System for Gram Stained Vaginal Smears, for complete Nugent scoring criteria.

The following shift table will be used to summarize the change in Nugent score from Visit 1 (Day 1) to Visit 6 (or final score).

Table 2 Nugent Score Shift Table

	Final Nugent Score	0–3	4–6	≥ 7	Total
Baseline Nugent Score	0–3				
	4–6				
	≥ 7				

Changes within each group and between groups will be reported.

10.10.2 Vaginal Colonization with Lactobacilli

Total lactobacilli (based on culture) will be scored as 1+, 2+, 3+, or 4+.

Colonization with *L. crispatus* strain CTV-05 (based on rep-PCR) will be scored as present or absent (frequency). Number and percent of subjects with positive CTV-05 in each treatment group will be presented. 95% confidence intervals will be calculated to evaluate any difference between the treatment groups.

The differences of these scores between Visit 1 (Day 1, Baseline) and Visits 3 and 6 for each subject will be evaluated within each group and between treatment groups.

10.10.3 *E. coli* Vaginal Colonization

The number (%) subjects with *E. coli* colonization in each treatment group will be summarized by treatment group and visit. 95% confidence intervals will be calculated to evaluate any difference between the treatment groups at a given visit.

10.10.4 Change in Vaginal Microbiota, as assessed by DNA amplification.

The number (%) of specific *Lactobacillus spp.* and uropathogens will be summarized by treatment group and visit. 95% confidence intervals will be calculated to evaluate any difference between the treatment groups at a given visit.

10.10.5 Safety and Tolerability.

The safety endpoints include specific solicited adverse events (AEs), all other reported AEs, serious adverse events (SAEs) and signs of irritation on pelvic examination. The adverse events emerging during the study, their severity and relation to study product will be recorded. Each event will be coded with system organ class and preferred term based on the Medical Dictionary for Regulatory Activities (MedDRA). Number (%) of subjects with AEs will be summarized by system organ class, preferred terms, and treatment group. Severity of AEs and relationship to study product will also be summarized by system organ class, preferred terms, and treatment group. SAEs and reasons for premature termination from study will be summarized by treatment group in frequency and percent. In addition, signs of irritation of the external genitalia, vagina or cervix from pelvic examination, along with their severity and relation to study product will be summarized by treatment group. Furthermore, symptoms and physical findings will be summarized.

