Many studies have confirmed that the critical event preceding a UTI is colonization of the vaginal introitus with gut microbiota, most commonly *E. coli* (5, 6). Women with recurrent UTI are more likely to be vaginally colonized with *E. coli* or other *Enterobacteriaceae* than women without recurrent UTI, and demonstrate prolonged periods of persistent colonization. Recent studies have verified these findings and have demonstrated a coincident loss of the normally predominant vaginal lactobacilli [10, 11, 12]. In a study in women of reproductive age, 15% of 302 women who had vaginal colonization with *L. crispatus* or *L. jensenii*, both H₂O₂ producers, were colonized with *E. coli* as compared with 27% of women who did not have these lactobacilli species present ($p = 0.01$) (7). This and other data suggest that H₂O₂-producing lactobacilli may have an important role in the maintenance of the normal vaginal ecology and in the prevention of vaginal colonization with *E. coli* and thus *E. coli*-induced UTI.

Mechanistic studies also support the ability of H₂O₂-producing lactobacilli to exclude *E. coli* vaginal colonization. Thus, Osset and colleagues showed that such lactobacilli are capable of competitive exclusion, blocking adherence of *E. coli* to vaginal epithelial cells (8). In addition, *L. crispatus* inhibits the growth of *E. coli* in both liquid and solid media through the action of H₂O₂. Finally, recent studies at the University of Washington have

shown that *L. crispatus* adheres extremely well to vaginal epithelial cells from women with recurrent UTI, suggesting it will colonize such women's vaginal epithelium (9).

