3.2.2 Secondary Objectives

1. To evaluate vaginal colonization with total *Lactobacillus* (endogenous and exogenous) in subjects receiving LACTIN-V versus placebo.
2. To evaluate vaginal colonization with *Lactobacillus crispatus* strain CTV-05 (the LACTIN-V strain of *Lactobacillus*).
3. To evaluate vaginal colonization with *E. coli* in subjects receiving LACTIN-V versus placebo.
4. To evaluate shifts in vaginal microbiota in subjects receiving LACTIN-V versus placebo, as assessed by Nugent score of vaginal gram stains at all visits.

5. To evaluate shifts in the composition of vaginal microbiota in subjects receiving LACTIN-V versus placebo, as assessed by qualitative and/or quantitative DNA amplification of stored vaginal fluid specimens from all visits.
6. To evaluate the safety of LACTIN-V over four months.

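### Vaginal E. coli culture is compared between arms only visit by visit, with no single treatment-effect estimate and no use of the pre-dose Visit 1 culture, so the mechanistic comparison is less precise than the data allow

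*Combined protocol and SAP*

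**What the plan says.** Secondary objective 3 (section 3.2.2) is: "To evaluate vaginal colonization with *E. coli* in subjects receiving LACTIN-V versus placebo". Section 10.3 sets the schedule: "Vaginal cultures of total lactobacilli and *E. coli* will be evaluated at Visits 1 through 6". Visit 1 is the randomization visit and its swabs are taken before the first applicator, so there is one pre-dose culture and five later ones.

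Section 10.10.3 plans two things. The number and percent with *E. coli* "colonization in each treatment group will be summarized by treatment group and visit", and "95% confidence intervals will be calculated to evaluate any difference between the treatment groups at a given visit". The *E. coli* row of Table 1 (section 10.8) gives the method as "95% confidence interval at Visits 1-6" and no test. No key visit, summary across visits, repeated-measures model or adjustment for Visit 1 culture is named.

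Other microbiology endpoints do use Visit 1. Section 10.10.1 plans a Nugent shift table from Visit 1 to Visit 6. For lactobacilli and CTV-05, section 10.10.2 says: "The differences of these scores between Visit 1 (Day 1, Baseline) and Visits 3 and 6 for each subject will be evaluated". Section 10.10.3 has no such sentence.

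**The concern.** Section 2.1 presents vaginal *E. coli* colonization as the step before UTI and its reduction as the way the product should work. The *E. coli* comparison is therefore the trial's randomized evidence on mechanism. The same section says that women with recurrent UTI "demonstrate prolonged periods of persistent colonization", so repeated cultures in one woman should be correlated and her pre-dose culture may predict her later ones.

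The plan uses neither feature. Each interval rests on one culture per woman, and five post-dose intervals come with no rule for reading them together. A real effect could be missed at every visit. Equally, one favorable visit could be quoted as the result.

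**Working it through.** **Plan's own figure.** The documents give no power, precision or error rate for *E. coli*. The only power figure, in section 10.4, concerns UTI: above 80% for a halving from 40% with 250 women. It reproduces as an inequality: 93.7% with no loss and 82.9% with 30% loss (two-sided 0.05).

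**Inputs**
- Planning rates: 27% and 15%, from section 2.1 (women without and with *L. crispatus* or *L. jensenii*). Treating these as placebo and LACTIN-V is an assumption.
- Women per arm: section 10.4 gives 250 in total, sections 4.3 and 5.1 give 276. The range used is 112 (250 less an assumed 10%: 125 × 0.9 = 112.5) to 138 (276/2).
- Within-woman correlation ρ between visits: not given. Main range 0.17 to 0.48, wider range 0 to 0.9, equal between all visits (assumed).
- Two-sided 5%, to match the 95% intervals.

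**One visit.** SE = √[(0.27×0.73 + 0.15×0.85)/n] = √(0.3246/n). Power = Φ(12/SE − 1.96), SE in points.
- n = 112: SE 5.38, power 61%.
- n = 125: SE 5.10, interval ±10.0 points, power 65%.
- n = 138: SE 4.85, power 70%.

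**Average of Visits 2 to 6, n = 112, constant effect.** Unadjusted SE = 5.38 × √[(1+4ρ)/5]. Adjusted for Visit 1, if Visit 1 has the same ρ with each later visit, SE = 5.38 × √[(1+4ρ)/5 − ρ²].

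| ρ | Unadjusted SE (power) | Adjusted SE (power) |
|---|---|---|
| 0.17 | 3.1 (97%) | 3.0 (98%) |
| 0.48 | 4.1 (83%) | 3.2 (96%) |
| 0.70 | 4.7 (73%) | 2.8 (99%) |

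The adjusted column is an approximation for a binary outcome.

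**Smaller effect, n = 112, SEs held as above, ρ 0.17 to 0.48**
- Partial colonization: section 4.2 reports 61% of women randomized to LACTIN-V colonized in LV-006. 0.61 × 12 = 7.3 points. Power at one visit: Φ(7.3/5.38 − 1.96) = 27%. For the average: from Φ(7.3/4.11 − 1.96) = 43% (unadjusted, ρ 0.48) to Φ(7.3/2.98 − 1.96) = 69% (adjusted, ρ 0.17).
- Fading: 12 points at Visits 2 to 4 and none at Visits 5 and 6 averages 3 × 12/5 = 7.2 points, with power 42 to 68%. A single on-dosing visit keeps its 61%, so here the average has no clear advantage in power over one on-dosing visit named in advance.

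**Chance that at least one of five post-dose intervals excludes zero with no true effect**
- Independent visits: 1 − 0.95⁵ = 22.6%.
- Normal approximation, equal correlation: 22.0% at ρ 0.17, 18.5% at 0.48, 14.9% at 0.7, 10.1% at 0.9.
- Simulated binary cultures, 27% prevalence, 125 per arm: 22.8% at an observed correlation of 0.18, 19.1% at 0.47.
- One prespecified estimate: 5%.

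**The case against.** The strongest reply is that nothing planned is invalid. Each visit's interval compares one culture per woman between randomized arms, so within-woman correlation does not bias it. Visit-wise reporting is also a natural choice when time course matters. Sections differ on whether weekly dosing lasts 8 weeks (3.4.1, 5.1) or 10 (4.1, 4.2, 10.1), and those passages must be reconciled. On either account Visits 5 and 6, at Weeks 14 and 18 in section 10.3, come after dosing. All of that stands. It supports keeping the visit profile, but it does not supply the missing overall estimate.

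Four stronger readings are tempting, and the documents do not support them.
- A reader might infer that the plan carries a false-positive rate of about 20%. It sets no alpha, test or success rule for this endpoint. The figure applies only if any one interval is taken as an effect, and stronger persistence lowers it towards 10%.
- A reader might infer that section 2.1 implies a 12-point treatment effect, and so near-certain power for the average. The 27% versus 15% contrast is observational, and not every treated woman is colonized.
- A reader might infer that the persistence statement guarantees a large gain from Visit 1 adjustment. Visit 1 falls 3 to 10 days after antibiotics, when section 4.3 expects the microbiota to be most disrupted, so it may predict less. The gain from averaging does not depend on it.
- A reader might extend the point to DNA amplification. The text of 10.10.4 has the same per-visit sentence, but Table 1 lists "CMH 95% confidence interval" there, so intervals are not the only planned method.

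**Conclusion.** The point holds for vaginal *E. coli* culture. Sections 10.10.3 and 10.8 plan only separate between-arm intervals at Visits 1 to 6, and both the repeated cultures and the pre-dose culture go unused in the comparison.

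At 112 per arm and ρ of 0.17 to 0.48, averaging alone cuts the SE by 24 to 42%, and by 40 to 45% with Visit 1 adjustment if Visit 1 is as correlated as the later visits. The gain in power depends on the true effect: large at a constant 12 points, moderate at about 7 points from partial colonization, and not assured against a well-chosen on-dosing visit if the effect fades. The selection risk of about 10 to 23% is conditional on how the intervals are read.

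The planning rates, numbers per arm and correlation are all assumptions. This is one of six secondary objectives; it bears on the mechanistic interpretation and leaves the primary UTI conclusion as it is.

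**What to change.** In section 10.10.3 and the *E. coli* row of Table 1:
- Name one between-arm estimate: the treatment effect averaged over Visits 2 to 6, from a repeated-measures model (GEE with robust standard errors) with Visit 1 *E. coli* status as covariate. State its scale; a risk difference would be comparable with the visit-wise intervals.
- Show the treatment-by-visit profile, because the later visits fall after dosing ends.
- Label the visit-wise intervals descriptive, and drop the between-arm comparison at Visit 1, which precedes dosing.

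The cost is a few lines of SAP text and one more model on data already to be collected. The average will understate the on-product effect if that effect fades, and the visit profile is there to show it. Calling the intervals descriptive without adding the estimate would deal with the selection risk but leave the loss of precision. The wording should be settled before unblinding.
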